8.2 Discontinuation From the Study

Withdrawal of consent for a study means that the subject does not wish to receive further protocol-required therapies or procedures, and the subject does not wish to or is unable to continue further study participation. Subject data up to withdrawal of consent will be included in the analysis of the study, and where permitted, publicly available data can be included after withdrawal of consent. The investigator is to discuss with the subject appropriate procedures for withdrawal from the study and must document the subject's decision to withdraw in the subject's medical records.

If a subject withdraws from the study, he/she may request destruction of any samples taken and not tested, and the investigator must notify Amgen accordingly (see [Section 12.6](#) for further details). Refer to the Schedule of Activities ([Table 2-1](#)) for data

to be collected at the time of study discontinuation and follow-up and for any further evaluations that need to be completed.

8.2.1 Reasons for Removal From Washout, Run-in or Invasive Procedures

Not applicable.

8.2.2 Reasons for Removal From Study

Reasons for removal of a subject from the study are:

- decision by sponsor
- withdrawal of consent from study
- death
- lost to follow-up

8.3 Lost to Follow-up

A subject will be considered lost to follow-up if he or she repeatedly fails to return for scheduled visits and is unable to be contacted by the study site.

The following actions must be taken if a subject fails to return to the clinic for a required study visit:

- The site must attempt to contact the subject and reschedule the missed visit as soon as possible and counsel the subject on the importance of maintaining the assigned visit schedule and ascertain whether or not the subject wishes to and/or is able to continue in the study.
- In cases in which the subject is deemed lost to follow-up, the investigator or designee must make every effort to regain contact with the subject (where possible, 3 telephone calls and, if necessary, a certified letter to the subject's last known mailing address or local equivalent methods). These contact attempts are to be documented in the subject's medical record.
- If the subject continues to be unreachable, he/she will be considered to have withdrawn from the study with a primary reason of lost to follow-up.
- For subjects who are lost to follow-up, the investigator can search publicly available records (where permitted) to ascertain survival status. This ensures that the data set(s) produced as an outcome of the study is/are as comprehensive as possible.

9. Study Assessments and Procedures

Study procedures and their time points are summarized in the Schedule of Activities (see [Table 2-1](#)).

As protocol waivers or exemptions are not allowed if an enrolled subject is subsequently determined to be ineligible for the study, this must be discussed with the sponsor immediately upon occurrence or awareness to determine if the subject is to continue or discontinue study treatment.

Adherence to the study design requirements, including those specified in the Schedule of Activities, is essential and required for study conduct.

9.1 General Study Periods

9.1.1 Screening and Enrollment

Informed consent must be obtained before completing any screening procedure or discontinuation of standard therapy for any disallowed therapy. After the subject has signed the informed consent form, the site will register the subject in the IRT and screen the subject in order to assess eligibility for participation. The screening window is up to 28 days from date of consent until enrollment.

All screening evaluations must be completed and reviewed to confirm that potential subjects meet all eligibility criteria. The investigator will maintain a screening log to record details of all subjects screened and to confirm eligibility or record reasons for screening failure (see Section 6.4), as applicable.

If a subject has not met all eligibility criteria at the end of the screening period, the subject will be registered as a screen fail. Screen fail subjects may be eligible for rescreening 1 time.

Rescreen subjects must first be registered as screen failures in IRT and subsequently registered as rescreens. Once the subject is registered as rescreened, a new 28-day screening window will begin. Subjects will retain the same subject identification number assigned at the original screening. If the rescreening period begins more than 28 days after the original signing of the informed consent form, all screening procedures, including informed consent, must be repeated.

9.1.2 Treatment Period

Visits will occur per the Schedule of Activities (Table 2-1). Subjects assessed as eligible for the study will be enrolled and must start study treatment within 3 days of enrollment. On-study visits may be completed within 3 days. The date of the first dose of protocol-required therapies is defined as day 1. All subsequent doses and study visits will be scheduled based on the day 1 date. Administration of protocol-required therapies is to be administered last during each visit that it is required, unless otherwise indicated in the Schedule of Activities.

After discontinuation from study treatment, subjects who do not have confirmed PD are required to continue disease response assessments and report new antimyeloma treatment and will be followed every 28 ± 7 days until first subsequent antimyeloma

treatment, death, loss to follow-up, withdrawal of full consent, confirmed PD, or end of study, whichever comes first.

9.1.3 Safety Follow-up

Upon discontinuation from the study treatment for any reason, a safety follow-up visit will be performed approximately 30 (+3) days after the last dose of study drug(s) unless the subject is lost to follow-up, has withdrawn consent, or has died.

9.1.4 Long-term Follow-up

After discontinuation from study treatment and the subject either starts new antimyeloma treatment or has PD, they enter long-term follow-up. Survival information will be collected as indicated in the Schedule of Activities ([Table 2-1](#)). Long-term follow-up may continue until end of study.

9.1.4.1.1 End of Study

The end of study date is defined as the date when the last subject across all sites is assessed or receives an intervention for evaluation in the study (ie, last subject last visit), including any additional parts in the study (eg, long-term follow-up, additional antibody testing), as applicable.

The end of study visit will occur for all subjects who have not discontinued from the study 4 years after last subject enrolled. This could either be a safety follow-up visit 30 (+3) days after last dose of study drug(s) or a final long-term follow-up survival assessment.

9.2 Description of General Study Assessments and Procedures

The sections below provide a description of the individual study procedures for required time points.

9.2.1 General Assessments

All of the assessments below and in the Schedule of Activities ([Table 2-1](#)) will be recorded on the eCRF.

9.2.1.1 Informed Consent

All subjects must sign and personally date the IRB/IEC approved informed consent before any study-specific procedures are performed.

9.2.1.2 Demographics

Demographic data collection including sex, age, race, and ethnicity will be collected in order to study their possible association with subject safety and treatment effectiveness.

Additionally, demographic data will be used to study the impact on biomarker variability and PK of the protocol-required therapies.

9.2.1.3 Medical History

The Investigator or designee will collect a complete medical and surgical history that started within 30 days prior to signing of the ICF. In addition, medical history will include collecting information on the subject's significant medical conditions, prior surgeries, and neuropathy history, dating back to the original diagnosis. Record all findings on the medical history eCRF. The current toxicity grade will be collected for each condition that has not resolved. Cardiovascular risk factors, which include family history of cardiovascular disease and smoking history, amyloidosis history, and contraception method will also be collected.

In addition to the medical history above, multiple myeloma history must date back to the original diagnosis. For subjects who are being referred to the research site, critical referral information will constitute multiple myeloma information from source notes.

9.2.1.4 Physical Examination

Physical examination will be performed as per standard of care. Physical examination findings should be recorded on the appropriate CRF (eg, medical history, event).

9.2.1.5 Physical Measurements

Height (in centimeters) and weight (in kilograms) should be measured without shoes.

Body surface area should be calculated using the Mosteller Formula (Mosteller, 1987):

$$\text{BSA (m}^2\text{)} = ([\text{height (cm)} \times \text{weight (kg)}] / 3600)^{1/2}.$$

9.2.1.6 Substance Abuse History

Obtain a detailed history of prior and/or concurrent use of tobacco.

9.2.1.7 Performance Status

The subject's performance status will be assessed using the ECOG PS (Section 12.9).

9.2.2 Efficacy Assessments

Disease assessments will be based on local laboratory data and local imaging obtained in accordance with the IMWG-Uniform Response Criteria (IMWG-URC) (Section 12.11) until confirmed PD (Section 9.2.2.6) irrespective of cycle duration including dose delays and treatment discontinuation as indicated in the Schedule of Activities (Table 2-1).

After discontinuation from study treatment, subjects who do not have confirmed PD are required to continue disease response assessments and report new antimyeloma

treatment and will be followed every 28 ± 7 days until first subsequent antimyeloma treatment, death, loss to follow-up, withdrawal of full consent, confirmed PD, or end of study, whichever comes first.

Disease response and progression assessments include: serum and urine protein electrophoresis (SPEP, urine protein electrophoresis [UPEP], respectively), SFLC, serum and urine immunofixation (SIFE, UIFE, respectively) (Section 9.2.2.1), quantitative IgA, IgD, or IgE (for subjects with IgA/IgD/IgE myeloma), bone marrow sample evaluation (Section 9.2.2.2), serum calcium, bone lesion assessment (Section 9.2.2.3) and extramedullary plasmacytoma evaluation (Section 9.2.2.5).

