The study is an open-label, phase 2 trial. Subjects may receive treatment until progression. Myeloma disease status will be monitored locally for response and progression per International Myeloma Working Group (IMWG) criteria (Kumar et al, 2016) every 28 ± 7 days from cycle 1 day 1 until confirmed progressive disease (PD), death, lost to follow-up, or withdrawal of full consent (whichever occurs first), regardless of cycle duration, dose delays or treatment discontinuation. Subjects with a suspected CR or better will have a bone marrow for minimal residual disease (MRD) assessment at 12 and 24 months (\pm 4 weeks) from start of treatment (unless a MRD assessment was performed within 4 months before planned assessment). Subjects who end study drug(s) without confirmed PD are required to complete disease response assessments and report new antimyeloma treatment every 28 ± 7 days until first subsequent antimyeloma treatment, death, lost to follow-up, withdrawal of full consent, confirmed PD, or end of study, whichever occurs first. Subjects who discontinue treatment and either start new antimyeloma treatment or have PD, will enter long-term follow-up every 12 weeks until death or end of study.

Number of Subjects

According to Protocol Amendment 3, approximately 85 subjects will be enrolled in the study, with approximately one-third of subjects in first relapse and two-thirds in second relapse. **In late 2021, enrollment was discontinued after 54 subjects were enrolled.**

Summary of Subject Eligibility Criteria

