5.1 Overall Design

The study is an open-label, phase 2 trial to assess efficacy and safety of carfilzomib, pomalidomide, and dexamethasone (KPd).

Eligible subjects will have relapsed or relapsed and refractory multiple myeloma after receiving 1 or 2 prior treatment regimens. Subjects must be refractory to lenalidomide and may have been previously exposed to an anti-CD38 antibody therapy. Subject is considered refractory if any of the following criteria is met:

- The best response reached during at least 1 regimen containing the drug of interest was stable disease or progressive disease
- The reason that the drug of interest was stopped was progression in at least 1 regimen
- The date of relapse/progression is after start date and within 60 days after stop date of the drug of interest in at least 1 regimen

According to Protocol Amendment 3, Approximately 85 subjects will be enrolled, with approximately one-third of subjects in the first relapse and two-thirds of subjects in second relapse. **In late 2021, enrollment was discontinued after 54 subjects were enrolled.** Subjects may receive treatment until progression. The regimens will be administered per Section 7.1.

All subjects will be assessed for multiple myeloma disease response according to the International Myeloma Working Group Uniform Response Criteria (IMWG-URC) (Section 12.11) every 28 ± 7 days from cycle 1 day 1 through death, confirmed PD, lost to follow-up, withdrawal of full consent (whichever occurs first), or end of study, regardless of cycle duration, dose delays or treatment discontinuation. Subjects who end study drug(s) before confirmed progressive disease (PD) are required to complete disease response assessments and report new antimyeloma treatment every 28 ± 7 days until first subsequent antimyeloma treatment, death, loss to follow-up, withdrawal of full consent, confirmed progress disease (PD), or end of study, whichever occurs first.

The individual subject disease response and disease progression for this study will be independently assessed by an Independent Review Committee (IRC) in accordance with

the IMWG-URC. The membership criteria and operational details of the IRC will be described in the IRC Charter. The IRC will centrally review the disease-related tests and assessments to evaluate disease progressions and responses without the knowledge of the investigator's disease assessments. The IRC assessment will be used for the analysis of the ORR.

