9.2.2.6 Progressive Disease Assessment

Confirmation of PD requires 2 consecutive assessments made at any time before the initiation of any new therapy*, as well as no known evidence of progressive or new bone lesions if radiographic studies were performed. Radiographic studies are not required to

satisfy these response requirements. Bone marrow, plasmacytoma, and skeletal survey assessments are not required to be confirmed by repeat testing.

* Every effort should be made to obtain 2 consecutive samples at any time prior to initiation of any new therapy. If not possible to obtain the second consecutive assessment to confirm disease progression before initiation of any new therapy, this confirmatory sample for disease progression may be obtained after the new therapy is initiated.

The assessments outlined in Section 12.11 are required for PD. Subjects will be considered to have PD if they meet the criteria for progression by a variable that was not considered measurable at baseline; however, for subjects who had a measurable serum or urine M-spike at baseline, progression cannot be defined by increases in SFLC alone (Kumar et al, 2016).

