
Number of doses of pomalidomide administered

It is defined as the total number of non-zero doses of pomalidomide a subject received during the treatment period of the study

Number of doses of dexamethasone administered

It is defined as the total number of non-zero doses of dexamethasone a subject received during the treatment period of the study

Overall Response (OR)

OR is the best overall confirmed response of partial response (PR), very good partial response (VGPR), complete response (CR), or stringent complete response (sCR).

Overall Response Rate (ORR)

Overall Response Rate (ORR) is defined as the proportion of subjects that reach the overall response among all subjects who received at least 1 dose of the carfilzomib.

Overall Survival (OS)

OS is defined as time from start of treatment until death from any cause.

$OS = (\text{Death date or date of censoring if censored} - \text{start of any study treatment date} + 1) / 30.4$

Subjects still alive will be censored at the date last known to be alive. If the date last known to be alive is after the date that triggers the analysis (ie, the data cutoff date), the subject will be censored at the analysis trigger date.

Progression Free Survival (PFS)

PFS is defined as the time from the first dose date of any study treatment until the first documentation of disease progression or death due to any cause, whichever occurs first in the absence of subsequent anticancer therapy and if not > 70 days from the last non-NE, post-baseline disease assessment. PFS will be censored at the last non-NE, post-baseline disease assessment or the earlier of the following, where applicable: (a) the last non-NE, post-baseline disease assessment prior to subsequent anticancer therapy, or (b) the last non-NE, post-baseline assessment followed > 70 days later by disease progression or death; otherwise, at first dose date. Disease progression is based on the IMWG-URC [2016].

PFS time in months= [(PD or death date, whichever occurs first) or date of censoring if censored– start of treatment date + 1] / 30.4.

Table 5-1. Conventions for Censoring for PFS

Situation	Date of Progression or Censoring	Outcome
No PD or death, no new anticancer treatment	Last visit; otherwise, first dose date of any study treatment	Censored
No PD or death, new anticancer treatment	Last visit prior to new treatment; otherwise, first dose date of any study treatment	Censored

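### Conflicting stop rules leave the confirmatory PD sample unscheduled after a therapy switch, so PFS and DOR may be censored at the visit that showed progression

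*Protocol*

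**What the plan says.** **When assessments stop.** Protocol 9.2.2 opens with disease assessments continuing "until confirmed PD (Section 9.2.2.6) irrespective of cycle duration including dose delays and treatment discontinuation". Protocol 5.1 has them run "through death, confirmed PD, lost to follow-up, withdrawal of full consent (whichever occurs first), or end of study, regardless of cycle duration". The synopsis (Overall Design) and SAP 3.1 have a similar rule. None of these lists new therapy as a stopping point. Each of the four places then adds a second rule for subjects who leave study treatment without confirmed PD. In Protocol 9.2.2 and 9.1.2 such a subject "will be followed every 28 ± 7 days until first subsequent antimyeloma treatment, death, loss to follow-up" and so on. Once new therapy starts, Protocol 9.1.4 moves the subject to long-term follow-up, for which Table 2-1 marks survival and no disease assessment.

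**What PD requires.** Protocol 9.2.2.6 states: "Confirmation of PD requires 2 consecutive assessments made at any time before the initiation of any new therapy". A footnote there, repeated in 9.2.2.1 and Appendix 11, asks sites to try to obtain both samples before the switch. Failing that, "this confirmatory sample for disease progression may be obtained after the new therapy is initiated". Some routes need only one assessment: "Bone marrow, plasmacytoma, and skeletal survey assessments are not required to be confirmed by repeat testing".

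**How the SAP counts it.** SAP Section 5 defines the PFS event as the earliest documented progression or death without prior subsequent therapy, with progression based on IMWG-URC. In Table 5-1, a subject with neither PD nor death who starts new anticancer treatment is censored at "Last visit prior to new treatment; otherwise, first dose date of any study treatment". A visit there means an evaluable post-baseline disease assessment. Footnote a censors whenever new therapy comes before PD. DOR follows the PFS censoring rule.

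**The concern.** The footnote foresees that some subjects will switch before the second sample and allows it to be drawn later. The rule for subjects off treatment ends their disease assessments at that switch. The sample is therefore permitted, but nobody is scheduled to take it, and a site that looks to the other stop rule is told to carry on.

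If the sample is missed and confirmation is required, a progression seen before the switch is recoded as a censoring on the day it was seen. That is informative censoring: the subject leaves the risk set because of the event. PFS and DOR then look longer than they are. None of the sensitivity analyses in SAP Table 9-2 targets this. The investigator and computational assessments change the assessor, and the per-protocol and modified safety sets (PFS only) change the population. None specifies a different handling of an unconfirmed PD followed by new therapy.

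**Working it through.** **1. The stop rules side by side.**

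| Place | Runs to confirmed PD despite discontinuation | Stops at new therapy once off treatment |
|---|---|---|
| Synopsis, Overall Design | yes | yes |
| Protocol 5.1 | yes | yes |
| Protocol 9.1.2 | not stated | yes |
| Protocol 9.2.2 | yes | yes |
| SAP 3.1 | yes | yes |

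Both rules cover the same subject: off study treatment, PD not yet confirmed, new therapy started. One continues and the other stops.

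**2. One subject traced through SAP Table 5-1.** A single M-protein or free-light-chain value meets PD, and the subject then switches.

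- (a) Second sample taken before the switch: PD is confirmed and is an event.
- (b) Second sample taken after the switch and confirming, PD dated to the first: event.
- (c) As (b), but PD dated to the second: new therapy now precedes PD, so footnote a censors at the last evaluable assessment before the switch, which is the PD-level visit.
- (d) No second sample, and a single assessment is accepted: event.
- (e) No second sample, and confirmation is required: the row for no PD with new treatment applies, and the subject is censored at the PD-level visit. A later death does not restore the event, because the row for no PD, new treatment and death also censors.
- (f) PD by marrow, plasmacytoma or skeletal survey: no repeat is needed, so this is an event.

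Only (c) and (e) lose an event. The SAP does not say whether confirmation is required for PFS and DOR, whether a confirmation after the switch counts, or which of the two dates is the PD date. It therefore does not separate (b) from (c), or (d) from (e).

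**3. Plan figures.** The documents state no power or event count for PFS or DOR, so there is none to reproduce. The power figures in Protocol Table 10-1 do reproduce by exact binomial. For 52 subjects, 38 responders are needed for ORR (69.2% and 91.8%) and 5 for MRD[-]CR (60.5% and 76.3%). Neither test uses a PD date.

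**4. Illustration of size.** Let *f* be the share of PFS events recoded as censorings at the event time. The documents give no value for *f*, so the range starts at 0. Let *m* be the true median under exponential PFS. The event hazard falls by the factor (1 − *f*), so

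- estimated median = *m* / (1 − *f*)
- estimated 12-month PFS = 0.5^(12(1 − *f*)/*m*)

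The values of *m* (7.2, 10.2 and 18 months) span the KPd trials in Protocol Table 5-1. The plan states no PFS assumption of its own. Worked case: 10.2/0.9 = 11.3 and 10.2/0.7 = 14.6.

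| *f* | *m* = 7.2: median; 12-month PFS | *m* = 10.2 | *m* = 18 |
|---|---|---|---|
| 0% | 7.2; 31.5% | 10.2; 44.2% | 18.0; 63.0% |
| 5% | 7.6; 33.4% | 10.7; 46.1% | 18.9; 64.5% |
| 10% | 8.0; 35.4% | 11.3; 48.0% | 20.0; 66.0% |
| 20% | 9.0; 39.7% | 12.8; 52.1% | 22.5; 69.1% |
| 30% | 10.3; 44.5% | 14.6; 56.5% | 25.7; 72.4% |

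A simulation with 52 subjects, 28-day visits, an assumed 20-month accrual and 12 months of follow-up after the last enrollment gave close 12-month rates (for *m* = 10.2: 46.2%, 48.1%, 52.2% and 56.9% at *f* = 5%, 10%, 20% and 30%). Mean events lost ran from 1.5 to 2.2 at *f* = 5%, and from 8.6 to 13.3 at *f* = 30%.

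**The case against.** The case on the other side is substantial.

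- **No waiting period is imposed.** The two PD assessments may be made at any time. The 28-day interval is the routine visit schedule and not a confirmation interval, so a repeat can be drawn just before the next line starts, and sites are asked to try. This stands. It narrows the affected group without emptying it.
- **The later sample is allowed, and one of the stop rules supports taking it.** True. But permission in a footnote is not a scheduled collection, and the other stop rule points the opposite way.
- **The SAP does not state that an unconfirmed PD is a non-event.** It uses the word confirmed for overall response and time to response, but not for PFS or DOR. This stands: the censoring is an inference. However, the same definition rests on IMWG-URC, which Protocol Appendix 11 summarizes as needing two assessments. The IRC charter and the sponsor standard behind the PFS wording may settle the matter, but neither is available here.
- **Many symptomatic relapses have a one-assessment route.** Bone imaging is repeated when symptoms suggest PD, and imaging, plasmacytoma and marrow findings need no repeat. This stands, and the illustrated range makes no allowance for it.

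A reader might infer that every subject who switches quickly is left unconfirmed and censored, or that 10% to 30% of progressions will be lost. The documents support neither. The first holds only on branches (c) and (e), and the second is a chosen range.

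**Conclusion.** The point holds as an inconsistency between stop rules together with a gap in the SAP. The bias is conditional. It needs an M-protein or free-light-chain progression, a switch before any repeat, and either a missing second sample with confirmation required or PD dated to a second sample taken after the switch. Where it occurs, PFS and DOR are overstated.

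The size is unknown and may be near zero. The figures above assume exponential PFS and loss unrelated to timing, and show only how the bias grows with the share lost. With 52 subjects, even 5% is about two events.

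The consequences are limited to secondary endpoints that carry no hypothesis test. The repair is cheap enough to be worth making.

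**What to change.** 1. **Reconcile the stop rules** in the synopsis, Protocol 5.1, 9.1.2 and 9.2.2, and SAP 3.1. A subject with an unconfirmed PD-level value should remain under disease assessment until the confirmatory local sample that 9.2.2.1, 9.2.2.6 and Appendix 11 already permit is obtained. No minimum interval should be added, since the current rule has none.
2. **Settle the PD date** in SAP Section 5 and Table 5-1. Confirmed PD is dated to the first of its two assessments, and a confirmation obtained after new therapy counts as an event on that first date.
3. **Add one PFS and DOR sensitivity analysis** to SAP Table 9-2. It would count a single PD-level assessment followed by new antimyeloma therapy or death as an event on the date of that assessment. This also covers samples that no longer confirm under the new therapy.

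The cost is clarifying text and one extra analysis run. Item 1 needs a protocol amendment after enrollment has closed. If that is not judged worthwhile, items 2 and 3 can be done in the SAP from data already collected. The downside is that a few unconfirmed values may count as PD in the sensitivity analysis, so PFS and DOR there may look slightly shorter.
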